4.1.2 Continuous Treatment

At the discretion of the investigator, patients may receive continuous treatment, at the same dose, upon completion of the DLT assessment period until disease progression, intolerable toxicity, withdrawal of consent, or termination according to the Principal Investigator's judgment or at the sponsor's request. Continuous treatment is defined as administration 3 times per week for 2 weeks followed by 1-week rest in a repeating 21-day cycle.

4.1.3 Study Procedures

Study procedures are listed and described in Table 2. Detailed descriptions of the time points for PK sampling, ECG, and vital signs evaluations in the first week of Cycle 1 is included in Table 3.

August 21, 2019 Confidential 35 / 74

Table 2: Study Assessment and Procedure Schedule

Assessment	Screen period		Cycle 1 (21 days)						Subseq	uent 21 days)	Follow-up/ End of Study
Day of Cycle	-21 to	1 ¹	2	3	5	8	10	12	1 ² (±3)	8 (±3)	30 to 35 days post last dose
Inform consent	X										
Review eligibility	X										
Demographic data	X										
Medical history/ baseline conditions	X										
Disease assessment Solid Tumors ³	X		Every 6 weeks \pm 5 days and as detailed in the footnote								
Disease Assessment AML ³	X		Every 6 weeks \pm 5 days and as detailed in the footnote								
Vital signs	X	X^4	X	X ⁴	X ⁴	X^4	X^4	X^4	X^4	X ⁴	X
Weight	X	X^4	X	X ⁴	X ⁴	X^4	X^4	X ⁴	X^4	X ⁴	X
Physical exam ⁵	X	X^4	X	X ⁴	X^4	X^4	X^4	X ⁴	X ⁴	X ⁴	X
ECOG performance review	X	X ⁴				X ⁴			X^4		X
12-lead ECG ⁶	X	X							X		X
Concomitant medications review	X	X				X			X		X
CT or MRI (solid tumor only)	X ⁷	Every 6 weeks ± 5 days									
Pregnancy test ⁸	X	X							X		
Hematology ⁹	X	X ⁴				X^4			X ⁴	X^4	X
Blood chemistry + amylase and lipase tests ⁹	X	X^4				X ⁴			X ⁴	X^4	X

August 21, 2019 Confidential 36 / 74

Assessment	Screen period		Cycle 1 (21 days)						Subsequent cycles (21 days)		Follow-up/ End of Study
Day of Cycle	-21 to	1 ¹	2	3	5	8	10	12	1 ² (±3)	8 (±3)	30 to 35 days post last dose
Bone Marrow Biopsy for patients with AML ¹⁰	X			Every	6 wee	eks ± :	5 days	and as	detailed i	n the footn	ote
Coagulation test ⁹	X										X
Urinalysis ¹¹	X								X		X
Adverse event	X						Хс	ontinuo	ous		
PK blood sample		X	X	X ¹²					X ¹²		
Study drug ¹³ administration		X		X	X	X	X	X	X	X	

Abbreviations: AML = Acute Myeloid Leukemia; BMI = Body Mass Index; CT = computed tomography; ECOG = Eastern Cooperative Oncology Group; MRI = magnetic resonance imaging; PK = pharmacokinetic

- 1. On Day 1 of Cycle 1, patients may need to stay at the clinical research unit overnight to complete PK sampling, safety observation and assessments.
- 2. For DLT cycle, patients will return for the end of the DLT assessment period (21 days from first dose of FN-1501) assessments on Day 1 of Cycle 2 (± 3 days). If additional cycles are planned, patients will start Day 1 dosing of next cycle after the assessments. For the last cycle, patients will return for the assessments.
- 3. Disease assessment every 6 weeks to coincide with every other cycle. Refer to Section 7.4 for details.
- 4. These assessments should be conducted, and the results should be available before study drug administration in each cycle. If assessments are conducted within 3 days prior to Day 1 of the cycle, the data can be recorded as Day 1 data of the cycle. See Table 3 for details. Height to be measured at Screening for BMI calculation.
- 5. A full physical exam will be conducted at screening, on Day 1 of each cycle and at follow-up. A full physical exam includes assessments of cardiovascular, respiratory, abdominal and neurological systems as well as lymph nodes/spleen, skin, oropharynx and extremities. Refer to Section 7.1.2 for details.

August 21, 2019 Confidential 37 / 74

6. ECGs to be performed prior to that days dose (if applicable) and after the patient has been supine for at least 10 minutes and should be performed with the patient in the same physical position for the duration of the test. ECG at Screening: performed in triplicate (5-10 min between readings). ECG at Day 1 of Cycle 1: performed in triplicate (5-10 min between readings) at the days indicated in Table 2 and time points and time windows detailed in Table 3. Cycle 2 Day 1: Perform in triplicate (5-10 min between readings) only if patient has a significant QTc prolongation, that is, a) > 500 msec; or b) increased by ≥ 60 msec over baseline; and/or c) decreased by 50 msec below pre-dose recording. If prolongation of QT or QT interval corrected for heart rate (QTc) is noted during the first 2 weeks, triplicate 12 lead ECGs will be conducted weekly during Cycle 2, and then once every 3 weeks before administration and 5-15 minutes after administration on Day 1 of every cycle from Cycle 3 onwards, until discontinuation of FN-1501 treatment. Refer to Section 7.1.3 for details on significant QTc prolongation.

- 7. Data obtained up to 42 days prior to Day 1 is acceptable.
- 8. Only in women of childbearing potential and additionally at the investigator's discretion.
- 9. In the event of neutropenia, thrombocytopenia, or \geq Grade 3 clinical chemistry toxicity, these assessments will be conducted as frequent as the investigator feels necessary until toxicity is resolved (\leq Grade 2). Refer to Table 6 for details on laboratory assessments.
- 10. Bone marrow biopsy for related assessments will be performed in patients with AML at Screening, every 6 weeks to coincide with the end of every other cycle, and at the end of the study or at time of relapse. Based on the patient's clinical condition, complete blood counts or bone marrow assessments may occur more frequently based on Investigator's judgment.
- 11. If urine protein is $\geq 2+$ by dipstick, then 24-hour urine for total protein and a random urine for total protein and creatinine will be collected and evaluated. See Section 7.1.1 for details.
- 12. Refer to Table 3 for details. PK sample must be collected pre-dose on Day 3 of Cycle 1 and pre-dose on Day 1 of Cycle 2 and as detailed in Table 3.
- 13. The investigational drug should be administered at approximately same time each time. The investigational drug is administered on Days 1, 3, 5, 8, 10, and 12 of each 21-day cycle. Not all treatment administration days are illustrated in the table.

August 21, 2019 Confidential 38 / 74

Table 3: Sampling Schedule (Day 1 of Cycle 1 to Day 1 of Cycle 2 Only; Refer to Table 2 for complete schedule)

Cycle		Cycle 1							Cycle 2				
Day of cycle		Day 1						Day 2	Day 3	Day 1			
		Post-Day 1 Dose Time Point:											
Time point ¹	Pre- dose	5 min	15 min	30 min	1 hr	2 hr	4 hr	6 hr	8 hr	12 hr	24 hr	48 hr (pre-Day 3 dose)	Pre-dose
PK sample	X	X	X	X	X	X	X	X	X	X	X	X ¹	X ¹
ECG ²	X				X	X							X
Vital signs ²	X	X	X	X	X	X	X	X	X	X	X	X	X

^{1.} Abbreviations: ECG = electrocardiogram; hr = hour; min = minute; PK = Pharmacokinetic Time point relative to end of infusion on Cycle 1, Day 1. Blood sample will be collected pre-dose on Day 3 of Cycle 1 and Day 1 of Cycle 2. See next page for sampling time windows.

2. Vital signs and ECG also collected at follow-up not shown (see Table 2 for details). Vital signs and ECG are predose unless otherwise indicated.

August 21, 2019 Confidential 39 / 74

Sampling Time Windows

The following time windows (relative to end of infusion) are allowed for PK sampling, ECG, and vital signs, as applicable:

• For pre-dose time points (Days 1, 3, and Cycle 2, Day 1): within 1 hr before dosing the planned study drug administration

• For 24 hr and 48 hr time points: +/- 1 hr., (prior to dosing on Day 3)

• For 2, 4, 6, 8 and 12 hr time points: +/- 30 min.

• For 30 min, 1 hr time points: +/- 15 min.

• For 15 min time point: +/- 5 min.

• For 5 min time point: +/- 3 min.

The actual time of PK sampling should always be recorded and entered in CRF.

August 21, 2019 Confidential 40 / 74

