Appendix 1: Signature of Investigator

Updated protocol title for consistency

August 21, 2019 Confidential 11 / 74

Synopsis

	·
Title:	A phase 1, multi-center, open-label, single-arm, dose-escalation, clinical study to evaluate the safety, tolerability, pharmacokinetics (PK) and anti-tumor activity of FN-1501 monotherapy in patients with advanced solid tumors or in relapsed/refractory Acute Myeloid Leukemia (AML)
Investigational drug:	FN-1501 lyophilized powder
Protocol No.	FN-1501-UP1
Clinical phase:	Phase 1
Number of patients:	Estimated 33 evaluable patients
Number of sites and locations:	3 sites in the United States (US) and Australia
Study cycle:	Screening period: Day -21 to Day -1. Treatment period: In the first cycle, a single dose of study drug will be administered three times a week on Days 1, 3, 5, 8, 10, and 12, with the last week off study drug (total 21 days). Subsequent treatment cycles will be 21 days and the study drug will be administered with the same dose and the same schedule as the first cycle. Follow-up period: 30 days after the last dose.
Objectives	
Primary	To evaluate the safety and tolerability of FN-1501 To determine the maximum tolerated dose (MTD) and recommended phase 2 dose (RP2D)
Secondary	To characterize the PK of FN-1501 and major metabolites To describe the preliminary anti-tumor activity of FN-1501

Study design:

This is a phase 1, first-in-human, open-label, multi-center, single-arm, dose escalation clinical study in patients with histologically or cytologically confirmed advanced solid tumors or relapsed/refractory AML, who cannot tolerate or do not respond to standard systemic therapy. It aims to determine the MTD and RP2D, evaluate the safety, tolerability, PK characteristics, and the preliminary anti-tumor activity of FN-1501.

August 21, 2019 Confidential 12 / 74

Eligible patients will receive a single intravenous infusion of study drug on Days 1, 3, 5, 8, 10, and 12 of a 21-day cycle. Dose limiting toxicity (DLT) assessment period is the first cycle of study treatment.

Starting dose, dose escalation scheme, and stopping criteria

- Dosing will begin at 2.5 mg once per day on the assigned days.

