4.1 Summary of Study Design

This is a phase 1, first-in-human, open-label, multi-center, single-arm, dose escalation clinical study in patients with histologically or cytologically confirmed advanced solid tumors or relapsed/refractory AML, who cannot tolerate or do not respond to standard systemic therapy.

Patients will be screened for eligibility for up to 21 days prior to entry into the study. The starting dose will be 2.5 mg/day on the assigned days. Dose escalation will use the traditional 3+3 design and follow a modified Fibonacci sequence until MTD is reached. Increments of 33% in the dose of FN-1501 will be undertaken after reaching 30 mg/day. Eligible patients will receive a single intravenous infusion of study drug on Days 1, 3, 5, 8, 10, and 12 of a 21-day cycle.

The DLT assessment period is 21 days from the first dose of FN-1501. Evaluation of a cohort of at least three (3) patients completing DLT assessment at any given dose level is required prior to determining the next dose level and dose regimen for the subsequent cohort.

August 21, 2019 Confidential 31 / 74

The highest dose under which one or no case of DLT is observed will be considered as MTD. If DLT cannot be observed, RP2D will be determined based on safety, preliminary anti-tumor activities and PK data.

Approximately thirty-three patients are expected to be enrolled.

After the first patient in the cohort receives the Cycle 1, Day 1 dose, subsequent patients in that cohort will not be dosed until the first patient has been evaluated for at least 48 hours to exclude unexpected acute toxicity. The continuous safety evaluation will be performed by investigators, the medical monitor, and the sponsor. A Safety Monitoring Committee (SMC) will determine dose levels to be administered and dose regimen during dose escalation based on the data available from the previous dose levels. If an MTD is not identified due to paucity of DLTs, the RP2D will be determined based on PKs, safety, tolerability, and preliminary efficacy.

If a patient wishes to continuously receive study treatment on completion of Cycle 1, the patient can continue study treatment in 21-day Cycle 2 and subsequent cycles (same as Cycle 2, all of 21 days' duration), defined as administration of 3 times per week for 2 weeks followed by 1 week rest, at the discretion of the investigator.

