4.1.1 Dose Escalation

The DLT assessment period is 21 days starting from the first dose of FN-1501. The study will follow a standard 3+3 dose escalation scheme and a modified Fibonacci sequence until the MTD is reached. Increments of 33% in the dose of FN-1501 will be undertaken after reaching 30 mg/day. Because of the dosage form (10 mg/vial), each dose will be rounded to numbers such as 2.5, 5, 10, 15, 22.5 mg/day, etc. At least three (3) patients will be enrolled into each cohort.

Additional patient(s), up to a maximum of four (4) patients in total, may be enrolled in a cohort if more than three (3) have been screened and are eligible for the cohort.

The DLT assessment and dose-escalation scheme will follow the same principle as stipulated for a standard 3+3 dose escalation design. For example, one (1) to three (3) additional patients will be enrolled if a DLT is observed in one (1) of first three (3) patients. No additional patients are required if a DLT is observed in one (1) of six (6) patients.

The starting dose will be 2.5 mg/day administered on the assigned days. One possible dose escalation scheme is presented in Table 1. Other dose levels may be evaluated during the study, depending on emerging data.

August 21, 2019 Confidential 32 / 74

Table 1: Suggested Dose Escalation Scheme

Dose Level/Cohort	Dose (mg/d)	Increase (%)
1	2.5	100
2	5	100
3	10	50
4	15	50
5	22.5	33
6	30*	33
7	40*	33

The actual dose levels and dose regimens administered in each step will depend on the data available from the previous level, as determined by the Safety Monitoring Committee.

As currently planned, if none (0) of the patients in one cohort experience DLT during the DLT assessment period, the dose to be administered in the next cohort will be increased by up to 100% (up to the 10 mg/d dose), by up to 50% (for the 10 mg and 22.5 mg doses) and by 33% thereafter, as determined by the SMC formed by the medical monitor, investigator, and sponsor representative.

The dose intervals will follow standard 3+3 escalation rules starting with the treatment of 3 patients as follows:

- 1. If 0 of 3 patients experiences a DLT, dose escalation will proceed to the next higher dose level at which 3 patients (up to 4) will be enrolled.
- 2. If 1 of 3 patients experiences a DLT, 3 more patients will be enrolled at the same dose level.
- 3. Escalation will continue if 0 or 1 of 6 patients experiences a DLT.

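### Table 2 sets no Day 22 floor for the end-of-DLT visit and the first Cycle 2 dose, so its ±3-day window can reach back into the 21-day DLT period

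*Protocol*

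**What the plan says.** Section 4.1.1 fixes the window that the 3+3 rule counts: "The DLT assessment period is 21 days starting from the first dose of FN-1501". Section 4.1 gives the same length. Section 4.1.2 places further treatment after it: "patients may receive continuous treatment, at the same dose, upon completion of the DLT assessment period". Section 4.1 ties Cycle 2 to the end of Cycle 1: "If a patient wishes to continuously receive study treatment on completion of Cycle 1, the patient can continue study treatment in 21-day Cycle 2". The Synopsis (Study cycle) describes Cycle 1 as six doses "with the last week off study drug (total 21 days"; under Study design it equates the DLT period with the first cycle.

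Table 2 in Section 4.1.3 heads the Day 1 column for subsequent cycles with ±3, and that column carries a study-drug mark. Footnote 2 reads in part "assessments on Day 1 of Cycle 2 (± 3 days). If additional cycles are planned, patients will start Day 1 dosing of next cycle", with dosing to come after those assessments. Three other notes bear on the point:

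- Footnote 13 gives the dosing days: "The investigational drug is administered on Days 1, 3, 5, 8, 10, and 12 of each 21-day cycle".
- Footnote 4 has its own allowance for early assessments: "If assessments are conducted within 3 days prior to Day 1 of the cycle, the data can be recorded as Day 1 data".
- The sampling windows after Table 3 state: "For pre-dose time points (Days 1, 3, and Cycle 2, Day 1): within 1 hr before dosing the planned study drug administration".

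**The concern.** The DLT window and the start of Cycle 2 should meet without overlap, and Section 4.1.2 says so. Table 2 and footnote 2 give the closing visit a minus side and let Cycle 2 dosing follow that visit. Neither sets a floor at Day 22. A site that books the visit early and doses afterwards can point to Table 2 in support while departing from Section 4.1.2.

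What is at stake is comparability within a cohort. Escalation rests on DLT counts in cohorts of three to six patients. If some of them receive seven or eight doses inside the counted window and others six, a DLT after an extra dose is charged to a dose level defined by a six-dose cycle. An early closing visit also means that the formal end-of-DLT assessment is made before the period has ended.

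**Working it through.** **Inputs.** DLT period: 21 days from first dose (Sections 4.1, 4.1.1). Dosing days in each cycle: 1, 3, 5, 8, 10, 12 (Table 2, footnote 13). Visit window: ±3 days (Table 2, column header and footnote 2). Illustrative dose: 30 mg/day (Table 1).

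**The plan's own figure.** With the first dose on study Day 1, the period covers Days 1 to 21 and nominal Cycle 2 Day 1 = 1 + 21 = Day 22. No Cycle 2 dose falls inside, so the window holds six doses: 6 × 30 = 180 mg. Drug-free days after the Day 12 dose: 22 − 12 − 1 = 9. Counting Day 22 as part of the window would place a Cycle 2 dose inside it even on the nominal schedule, so Days 1 to 21 is the sensible convention.

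**Shifted visit.** If the dose moves with the visit by *s* days, Cycle 2 Day 1 = 22 + *s*. Cycle 2 doses then fall 0, 2, 4, 7, 9 and 11 days later. Count those on or before Day 21.

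| Shift *s* | Cycle 2 Day 1 | Cycle 2 doses inside Days 1–21 | Total doses inside | mg inside at 30 mg/day | Drug-free days after Day 12 |
|---|---|---|---|---|---|
| −3 | Day 19 | Days 19, 21 | 8 | 8 × 30 = 240 | 6 |
| −2 | Day 20 | Day 20 | 7 | 7 × 30 = 210 | 7 |
| −1 | Day 21 | Day 21 | 7 | 7 × 30 = 210 | 8 |
| 0 | Day 22 | none | 6 | 180 | 9 |
| +1 to +3 | Days 23–25 | none | 6 | 180 | 10–12 |

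The overlap comes only from the minus side.

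**Assessments-only reading.** If ±3 moves the visit but not the dose, the closing visit can still fall on 22 − 3 = Day 19, leaving Days 20 and 21 after it. Footnote 4 gives the same earliest day for the assessments that carry it: 22 − 3 = Day 19.

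**The case against.** The best counter-argument is that ±3 was never a dosing window.

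- The neighbouring Day 8 column also carries ±3 and a study-drug mark. Applied literally to dosing, it would let the Day 8 dose fall on Day 5 or Day 10, both of which already have a scheduled dose. The header therefore cannot be a literal dosing window throughout the table.
- In footnote 2 the ±3 grammatically qualifies the return for assessments. The dosing sentence has no window of its own and does not say that dosing is on the same day.
- The one-hour rule ties the pre-dose samples to the dose, but it does not say on which calendar day the dose may be given.
- Sections 4.1 and 4.1.2 can be read as supplying the missing floor.

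All of this stands, and it is why the point is an inconsistency with a possible harmonising reading. A reader might infer that the protocol plainly authorises dosing on Day 19; the text does not go that far. A reader might also infer that the Synopsis is flatly contradicted. That holds only in part: the rest week and 21-day total conflict with an early dose, but a DLT period equal to the first cycle could simply end when Cycle 2 begins.

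Two things remain. Footnote 4 already lets many of the Day 1 assessments be done up to three days early, so an assessments-only reading makes the minus side of ±3 largely redundant for them. And that reading still allows the DLT-closing visit before the window has closed.

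**Conclusion.** The point holds as a minor inconsistency. Table 2 and footnote 2 set no Day 22 floor. Read naturally, they let the end-of-DLT visit and the dose after it occur from Day 19, which does not fit Section 4.1.2 or the 21-day period in Sections 4.1 and 4.1.1. The size is one extra dose in the window at −1 or −2 days and two at −3 days, at most one third above plan (8 against 6). The dose counts assume that the dose moves with the visit and that the window is Days 1 to 21; the early closing visit does not need the first assumption.

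A reader might go on to infer that escalation decisions or the maximum tolerated dose would be wrong. The documents do not support that. Nothing shows how often the minus side would be used, and a DLT after an extra dose would still count, which errs towards caution. Nor does an early visit mean that toxicity goes unseen: adverse events are collected continuously, footnote 9 adds laboratory tests when toxicity arises, and the nominal schedule has no routine panel between Day 8 and Day 22 anyway.

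**What to change.** For Cycle 2 Day 1 only, change the window to 0 to +3 days. State in footnote 2 that no Cycle 2 dose is given before study Day 22 and that the end-of-DLT evaluation is not completed before Day 21. Add a cross-reference in footnote 4 so that its three-day look-back is not used to close the DLT evaluation earlier than that. Keep ±3 days for later cycles.

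The change affects a column header and two footnotes and adds no procedure. The cost is slightly less scheduling freedom at one visit, where three days of flexibility remain on the plus side.

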4.1.4 Study Stopping Rules

The estimated duration of the study is contingent on the number of dose levels evaluated in the dose escalation. The study will be discontinued in the event of any new findings that indicate a relevant deterioration of the risk-benefit relationship that would render continuation of the study unjustifiable, or for administrative reasons by the Sponsor.

4.2 Selection of Study Population

4.2.1 Inclusion Criteria

Each patient must meet all the inclusion criteria for this study at the time of starting study treatment:

- 1. Male and female 18 years old and above
- 2. Able to understand and sign informed consent form
- Patients with histologically or cytologically confirmed advanced solid tumors
 who have relapsed or refractory disease or relapsed/refractory AML for which no
 standard therapies expected to produce clinical benefit to the patient are available
- 4. Patients with diagnosed solid tumors must have at least one lesion that is measurable per RECIST v1.1 criteria
- Patients with relapsed or refractory AML must be diagnosed with AML based on World Health Organization (WHO) criteria (≥ 20% blasts in bone marrow)
 Patients with acute promyelocytic leukemia are excluded.
- 6. Eastern Cooperative Oncology Group (ECOG) Performance Status 0 or 1
- 7. Have discontinued all previous cancer therapies for at least 21 days (for solid tumors) or at least 7 days (for AML) or 5 half-lives prior to study treatment, whichever is shorter, and recovered from the acute adverse effects of therapy
- 8. Expected to survive at least 2 to 3 months
- 9. Left ventricular ejection fraction (LVEF) \geq 50% and QTc interval \leq 450 ms
- 10. Women shall meet either of the following conditions before enrollment
 - Infertile, defined as having a bilateral oophorectomy (ovariectomy), or a bilateral tubal ligation, or being post-menopausal for at least 1 year
 - For those of childbearing potential, they should have a negative serum pregnancy test during screening, agree to refrain from lactation, and use effective contraception such as hormonal methods associated with inhibition of ovulation, condom, intra-uterine device, surgical sterilization (including partner's vasectomy) or sexual abstinence during the study and 30 days after the last administration of study drug
- 11. Men who are engaging or plan to engage in sexual activity with a female of childbearing potential must either have a prior vasectomy or agree to use effective contraception such as condoms, sexual abstinence and appropriate methods taken by their partner(s) during the study and 90 days after the last dose

August 21, 2019 Confidential 41 / 74

- 12. Patients must have adequate organ functions as indicated by the following screening laboratory values:
 - Serum total bilirubin $\leq 1.5 \times ULN$ (Serum total bilirubin can be $\leq 3.0 \times ULN$ if patients have hemolysis or congenital hemolytic diseases)
 - Creatinine < 1.5 × ULN or estimated creatinine clearance ≥ 50 mL/min
 - AST and ALT \leq 2.5 × ULN (AST and ALT can be \leq 5 × ULN for patient with liver metastases)
 - ANC $\ge 1.5 \times 10^9/L$
 - Platelets $\geq 100 \times 10^9/L$
 - Hemoglobin \geq 9 g/dL or \geq 5.6 mmol/L (Note: Criteria must be met without a transfusion within 2 weeks of obtaining the sample)

Note: Laboratory requirements for complete blood counts (hemoglobin, ANC, and platelets) do not apply to AML patients

